--	--

	
stored as a back-up. For participants who entered in the blinded version and then were unblinded and vaccinated, baseline serology will not be performed again, taking the values from the baseline visit performed at the first visit.
 

• For linking purposes, each participant will be assigned a treatment identification number. The number of each administered treatments must be recorded in the eCRF.

• Injection of study vaccine After completing all prerequisite procedures prior to injection, one dose of the assigned vaccine will be administered IM in the deltoid muscle, preferable of the non-dominant arm. If the investigator or delegate determines that the participant's health on the day of administration temporarily precludes administration, the visit will be rescheduled within 1 week. There will be a 15-minute wait after each vaccination to monitor for any rare anaphylactic reaction. At Day 56 after first vaccination, all participants will get a second injection of the investigational vaccine (Second Injection Visit)

• Safety participant contacts Every 4 Weeks for 52 weeks there will be telephone calls following vaccination. They will be used to continuously collect any SAE and MAE data. Participants can report any AE they experience at any time during the study period; however, only SAE and MAE will be entered into the eCRF. In-person visits will occur for Day 28 visit (to collect solicited and unsolicited events, Day 56 (Second Injection Visit), Day 84 and Week 24, and Week 52 visits.

• Efficacy participant contacts All participants will have efficacy participant contacts weekly, for 52 weeks following vaccination. There will be approximately 52 efficacy participant contacts. All efficacy participant contacts will be emails, although other methods such as phone calls or text messages, if preferred, are acceptable. Each participant contact needs to be recorded in the study electronic case report form. The purpose of these participant contacts is to ask if the participants had any symptoms of illness they may be experiencing, regardless of severity. Any possible COVID-19 relevant symptoms will trigger laboratory testing for SARS-CoV-2 infection.

• Illness participant contact visits (Confirmed or suspected infection during study) Participants will be provided detailed instructions regarding the signs and symptoms of COVID-19 disease at each participant contact and will be instructed to seek medical attention and notify study staff should symptoms occur. Symptoms of interest include fever, cough, difficulty breathing, diarrhea, nausea, vomiting, prolonged fatigue, respiratory symptoms, chills, myalgia, sore throat, headache, congested/runny nose, pneumonia, difficulty swallowing, anosmia/ageusia (loss of sense of smell/taste), and neurological events. During the observation period of the study, if any of these symptoms develop in a participant, he/she should immediately follow local procedures for care of suspected COVID-19 illness and contact the study team. If a COVID-19 infection is found during the study, a case investigation will be undertaken according to locally recommended procedures.

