- **Check and record prior and concomitant medication/vaccines**

Prior medications and concomitant medication/injection must be checked and recorded in the eCRF. Prior medications should include any medication taken by the participant within 14 days prior to screening. Participants will be asked to avoid over-the-counter medications such as antipyretics (e.g., acetaminophen) and anti-inflammatory medications (e.g., ibuprofen, naproxen) in the 12 hours before study vaccine receipt but will be allowed to take these over-the-counter medications as needed to treat fever or other adverse events after vaccination. Usage of these over-the-counter medications will be recorded as concomitant medications and linked to the adverse event collected as solicited or unsolicited events according to the symptom.

- **Check and record intercurrent medical conditions**

Any medical conditions that have arisen are recorded in the eCRF.

- **Treatment number allocation**

The treatment number will be allocated within each step. The number of each administered treatment must be recorded in the eCRF.

- **Injection of study vaccine**

After completing all prerequisite procedures prior to the active vaccine injection, one dose of the assigned vaccine will be administered IM, in the deltoid muscle, preferable of the non-dominant arm. If the investigator or delegate determines that the participant's health on the day of administration temporarily precludes administration, the visit will be rescheduled within 1 week. There will be a 15-minute wait after each vaccination to monitor for any rare anaphylactic reaction. A second injection, of active vaccine Ad5-nCoV, will be administered to all participants on Day 56.

- **Safety participant contacts**

Every 4 weeks there will be telephone calls (Weeks 8-52) to continuously collect any SAE and MAE data. Participants can report any AE they experience at any time during the study period but only SAE and MAE will be entered into the eCRF. Safety participant contacts will occur at First Injection Visit (for 15 minutes post-vaccination), Day 28 (to collect the diary), Day 56 (Second Injection Visit), Day 84 (to collect the diary), Month 4, 5, 6, 7, 8, 9, 10, 11, and 12. Safety participant contacts will be a telephone call for Months 2, 3, 4, 5, 7, 8, 9, 10 and 11, and as an in-person visit on Month 1 (Day 28), Month 2 (Day 56), Month 3 (Day 84), Month 6 (Week 24), and Month 12 (Week 52).

- **E-diary and Diary Cards**

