Participants will be provided with access to an e-diary or a paper diary card and a thermometer, and instructions about how to use them. The use of an e-diary instead of a paper diary card is dependent on the study site. Participants will be asked to record solicited AE for 7 days after receiving the vaccination, and unsolicited AE for 28 days, in their diary. The completed e-diary and diary cards will be reviewed, and data collected at the 28-Day safety in-person visit. A new diary will be provided at Day 56 and collected at Day 84. Non completion of the e-diary or diary cards will be investigated with the participant through telephone call(s) or any other convenient procedure. All data collected from the e-diary and diary cards will be uploaded into the eCRF.

- **Efficacy participant contacts**

All participants will have efficacy participant contacts weekly for 52 weeks following vaccination. There will be approximately 52 electronic efficacy participant contacts. All efficacy participant contacts will be text messages, although other electronic method such as by phone, e-mail, the Internet is suitable, if preferred. Each participant contact needs to be recorded in the study electronic case report form. The purpose of these participant contacts is to serve as a reminder to participants to report any symptoms of illness they may be experiencing, regardless of severity. Any possible COVID-19 relevant symptoms (e.g., fever, cough, shortness of breath, etc., according to WHO case definitions; see Section 3.8) will trigger laboratory testing for SARS-CoV-2 infection.

- **Illness participant contact visits (Confirmed or suspected infection during study)**

Participants will be provided detailed instructions regarding the signs and symptoms of COVID-19 disease at each participant contact and will be instructed to seek medical attention and notify study staff should symptoms occur filling the illness visit form and completing the eCRF. The form should be updated and sent and sent when the case meets the definition of severe COVID, and when the case resolves. Symptoms of concern include cough, fever, diarrhea, prolonged fatigue, respiratory symptoms, pneumonia, difficulty swallowing, loss of sense of smell and neurological events. For symptoms of interest, please refer to 3.8 efficacy participant contact.

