#### Time period for detecting and recording adverse events and serious adverse events

All AEs starting within 28 days following administration of the dose of the study product must be recorded into the appropriate section of the eCRF, irrespective of intensity or whether or not they are considered injection related.

The time period for collecting and recording SAEs and MAEs in all participants will begin at the first receipt of study product/comparator and will end on Day 364.

All AEs/SAEs leading to withdrawal from the study will be collected and recorded from the time of the first receipt of study product. SAEs that are related to the investigational product will be collected and recorded from the time of the first receipt of study product/comparator until the participant is discharged from the study.

In addition to the above-mentioned reporting requirements and in order to fulfill international reporting obligations, SAEs that are related to study participation (i.e. protocol-mandated procedures, invasive tests, a change from existing therapy) will be collected and recorded from the time the participant consents to participate in the study until she/he is discharged from the study.

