**Post-Study adverse events and serious adverse events**

A post-study AE/SAE is defined as any event that occurs outside of the AE/SAE reporting period. Investigators are not obligated to actively seek AEs or SAEs in former study participants. However, if the investigator learns of any SAE at any time after a participant has been discharged from the study, and he/she considers the event reasonably related to the investigational product, the investigator will promptly notify the Study Contact for Reporting SAEs.

**Evaluation of adverse events and serious adverse events****Active questioning to detect adverse events and serious adverse events**

As a consistent method of collecting AEs, the participants should be asked a non-leading question such as:

*'Have you acted differently or felt different in any way since receiving the product or since the last visit?'*

When an AE/SAE occurs, it is the responsibility of the investigator to review all documentation (e.g. hospital progress notes, laboratory and diagnostics reports) relative to the event. The investigator will then record all relevant information regarding an AE/SAE in the eCRF. The investigator will attempt to establish a diagnosis pertaining to the event based on signs, symptoms, and/or other clinical information. In such cases, the diagnosis should be documented as the AE/SAE and not the individual signs/symptoms.

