#### **Secondary Safety Objective Endpoints**

- The incidence of a decrease in CD4+ cell count by  $\geq 20\%$  at 24 and 52 weeks after vaccination
- The delta in the CD4/CD8 rate compared to the basal value.

All SAEs will be listed and summarized by groups.

For each participant, the individual local events will be aggregated into a combined event "Local", which is the maximum severity of the individual local events. For each participant, the individual general events will be aggregated into a combined event "General", which is the maximum severity of the individual general events. An aggregate event "Any" will be defined as the maximal severity of the combined events "Local" and "General". In addition to being graded for severity as mild, moderate or severe, the severity of all events will be graded as "Any", which will include mild, moderate or severe events, and "Significant" which will include moderate or severe events.

All statistical tests on safety performed will be 2-sided with Type I error of 5%. Missing values will not be included in the safety analyses, and there will be no imputation of missing values. No adjustments will be made for multiple comparisons.

For the analysis of proportions, binomial point estimates and exact binomial confidence intervals will be calculated.

Fisher's Exact Test will be used to assess differences in rates of adverse events between treatment and control groups.

In addition, all safety data will be analysed descriptively, including unsolicited events collected through the end of the observation period.

The Safety analysis will be performed based on the intent-to-treat cohort and per-protocol cohort.

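### The safety-contact text limits eCRF entry to SAEs and MAEs with no time limit, contradicting the rule that every AE starting within 28 days of a dose is recorded

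*Protocol*

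**What the plan says.** Two parts of the protocol give different entry rules.

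- **Section 5.1, Safety participant contacts.** The paragraph opens with "Every 4 weeks there will be telephone calls (Weeks 8-52) to continuously collect any SAE and MAE data" and continues: "Participants can report any AE they experience at any time during the study period but only SAE and MAE will be entered into the eCRF". It then lists the contacts it covers, among them the in-person visits at the first injection, Day 28, Day 56 and Day 84.
- **Synopsis, Study design, Safety participant contacts.** The rule is the same: "Participants can report any AE they experience at any time during the study period; however, only SAE and MAE will be entered into the eCRF". Here the four-weekly calls run for the whole 52 weeks, and the Day 28 visit is described as the occasion for collecting solicited and unsolicited events.
- **Section 7.2, time period for detecting and recording AEs.** "All AEs starting within 28 days following administration of the dose of the study product must be recorded into the appropriate section of the eCRF", whatever the intensity or suspected cause.
- **Section 7.2, active questioning.** As the uniform way of collecting AEs, "the participants should be asked a non-leading question such as" the example printed there. The investigator then records the event in the eCRF, with no restriction to diary-reported events.
- **Section 7, Table 3.** Unsolicited AEs are reported up to Day 28, counted from the first injection visit. After that, until Week 52, only SAEs and MAEs are reported.
- **Section 5.1, E-diary and Diary Cards.** "All data collected from the e-diary and diary cards will be uploaded into the eCRF". A second diary covers Day 56 to Day 84.

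The incidence of unsolicited AEs within 28 days is a primary safety endpoint (Section 9.3.3). The synopsis version of that endpoint adds that the period follows each vaccination.

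**The concern.** Take a non-serious AE that needs no medical attention, starts within 28 days of a dose, and is told to staff at a visit or call but never written in the diary. Section 7.2 says to enter it; the safety-contact text says not to. A site can follow either and claim to be on protocol.

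The choice matters because this is the kind of event that the primary unsolicited-AE endpoint counts. Any loss goes one way, towards a lower incidence. It could also differ between the four sites planned in Section 4. Section 9.3.3 excludes missing values and imputes nothing, so the analysis would not repair it.

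**Working it through.** The plan gives no figure on this point to reproduce. The check is a comparison of the texts plus day arithmetic.

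**Step 1. What each place directs for a non-serious, non-attended AE that is told to staff but is not in the diary.**

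| Place | Starts Day 0–28 (after dose 1) | Starts Day 56–84 (after dose 2) |
|---|---|---|
| Synopsis, Safety participant contacts | Not entered | Not entered |
| Section 5.1, Safety participant contacts | Not entered (no time limit; Day 28 visit listed) | Not entered |
| Section 7.2, time period | Entered | Entered, if its singular reference to the dose means each dose |
| Section 7.2, active questioning | Entered | Entered |
| Table 3 | Entered | Literally not entered: the days fall in the column after Day 29 |

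The conflict exists in both windows. After dose 2, Table 3 read literally sides with Section 5.1.

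**Step 2. Can the restriction be read as applying only after the AE windows have closed?** The inputs are the call period in Section 5.1 (Weeks 8–52), dose 2 at Day 56, and the 28-day window.

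- Week 8 = 8 × 7 = Day 56, which is the day of dose 2.
- The dose 2 window ends at 56 + 28 = Day 84 = Week 12.
- Week 52 = 52 × 7 = Day 364.

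The whole window (Day 56–84) lies inside the call period (Day 56–364). In the synopsis the calls span all 52 weeks, so the dose 1 window is inside as well. Timing alone does not resolve the conflict.

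**Step 3. Which events are exposed?** Diary entries are uploaded under either rule, so only events learned outside the diary are affected. The protocol foresees at least one route to them: an incomplete diary is followed up by telephone or another convenient means. A second route arises if the diary closes at the collecting visit, which is an assumption because the protocol does not say. With the ±7-day visit windows in Table 1:

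- Dose 1 at Day 0, Day 28 visit held at Day 21: 28 − 21 = 7 days of the window uncovered.
- Dose 2 at Day 56, Day 84 visit held at Day 77: 84 − 77 = 7 days.
- Dose 2 at Day 63, that visit held at Day 77: (63 + 28) − 77 = 14 days.

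Under that assumption, 0 to 14 days of a 28-day window fall outside the diary. This is exposure time, not a count of lost events.

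**Step 4. Size of the effect.** It would need the share of unsolicited AEs learned only outside the diary and the share of sites following Section 5.1. The protocol gives neither.

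**The case against.** The strongest reply is that Sections 7.1 and 7.2 are the dedicated AE-recording rules and are phrased as obligations, while the Section 5.1 sentence belongs to a paragraph on SAE and MAE telephone calls. Within Section 5.1's sentence, the reference to any time in the study describes when participants may report, not what sites enter. The same paragraphs describe the Day 28 visit as collecting unsolicited events (synopsis) and the Day 28 and Day 84 visits as collecting the diary (Section 5.1). Their authors therefore cannot have meant to exclude all non-serious AEs.

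Most of this stands. A reader might infer that AEs learned outside the diary simply drop out of the primary endpoint. The documents do not support that: Section 7.2 requires their entry, and the loss occurs only where a site lets the safety-contact sentence prevail.

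Two parts of the reply do not stand. The entry restriction itself carries no time limit, and its contact period contains the full dose 2 window. Table 3 settles the matter for dose 1 but, read literally, points the wrong way for dose 2.

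A reader might also fault Section 9.3.3 for planning to describe safety data "including unsolicited events collected through the end of the observation period", on the ground that nothing unsolicited is collected after Day 28. That is not correct. Section 7.1 classes every AE that is not solicited as unsolicited, and Section 7.2 collects SAEs and MAEs to Day 364. The sentence describes data that will exist.

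**Conclusion.** The contradiction is real, appears in two places, and affects the data behind a primary safety endpoint. It is an inconsistency in the recording instructions. It does not show that the protocol as a whole prescribes the loss of events.

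The exposed class is narrow: non-serious, non-attended AEs that start within 28 days of a dose, are learned outside the diary, and occur at a site that follows Section 5.1 over Section 7.2. For those events the effect is under-recording in one direction, possibly site-dependent.

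The amount cannot be estimated from the documents. One could assume a true incidence of 30% with 10–30% of events reported only verbally (at most one event per participant), and obtain 0.30 × (1 − 0.10) = 27% down to 0.30 × (1 − 0.30) = 21% at such sites. Both inputs are invented, so the result only restates them and should not be cited as the size of a bias. The correction is still worth making, because it is nearly free and removes a choice that sites should not have.

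**What to change.** - In the safety-contact paragraphs of the synopsis and Section 5.1, replace the restriction with: all AEs starting within 28 days after either dose are entered in the eCRF however they are learned; outside those periods only SAEs and MAEs are entered.
- In Section 7.2 (time period for detecting and recording), change the singular reference to the dose so that it covers each dose.
- In Table 3, make explicit that the solicited and unsolicited periods restart at the second injection, so that Day 56 to Day 84 is not read as limited to SAEs and MAEs.
- Leave the Section 9.3.3 sentence on unsolicited events to the end of the observation period unchanged. Restricting it to 28 days would remove its coverage of later unsolicited SAEs and MAEs.

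The cost is a few sentences, a memo to sites and slightly more eCRF entry. No visit, sample or analysis changes.

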**Safety Analysis****Primary Safety Endpoint:**

- The incidence of solicited adverse reactions within 7 days after vaccination.
- The CD4 / CD8 ratio delta compared to baseline.
- The incidence of unsolicited adverse events within 28 days after each vaccination.
- The incidence of detectable HIV viral load 24 and 52 weeks after vaccination
- The incidence of serious adverse events (SAE) and medically attended adverse events (MAE) within 52 weeks after vaccination in all participants.

Data from all participants will be used to assess the primary safety endpoint.

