  - Participants will donate approximately 25mL of whole blood on First Injection Visit, Day 28, Day 84 and Week 24, and Week 52, as described above. Whole blood will be separated into serum, and then aliquoted. These in-person visits will occur at participants' local study site. A baseline antibody titer against SARS-CoV-2 will be established from the blood sample collected on First Injection Visit, as outlined in the "baseline serology" description. In addition, these samples will also be used to evaluate for additional immunogenicity objectives. Serum collected will be analyzed for the seroconversion rate of S-RBD IgG antibody, GMT of S-RBD IgG antibody, GMI of S-RBD IgG antibody, seroconversion rate of pseudo-virus neutralizing antibody, GMT of pseudo-virus neutralizing antibody, and the GMI of pseudo-virus neutralizing antibody at Day 28, Day 84, Week 24, and Week 52. The second aliquot will be shipped by the central laboratory to Nexelis Laboratories, where it will be stored as a back-up.
  - **Blood collection for ELISpot and ICS measurement**
    - In a subset of approximately 50 participants, approximately 30mL of whole blood will be collected from participants on First Injection Visit, Day 28, Day 84 and Week 24, and Week 52, as described above. TNF, IL-4, IL-5, IL-13 will be measured by ICS on Day 28, Day 84 and Weeks 24 and 52 after vaccination. PBMC will be shipped on dry ice to Nexelis Laboratories (Canada).

- **Final serology**

Participants will have an in-person visit on Month 12. Approximately 25 mL of whole blood will be collected from each participant and separated for serum into two aliquots. The first aliquot will measure antibodies against SARS-CoV-2, at Nexelis laboratories. The second aliquot will be shipped by Nexelis laboratories to the Sponsor, where it will be stored as a back-up. The one-year antibody levels measured against SARS-CoV-2 will be compared to

the participant's baseline levels to evaluate the exploratory efficacy analysis against asymptomatic infection.

*The visit window for immunogenicity in-person visits of Day 28 and Day 84 is +/- 7 days.  
The visit window for immunogenicity in-person visits of Week 24, and Week 52 is +/- 14 days*

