### **9.3.3 Safety Analysis**

#### **Primary Safety Endpoint:**

- The incidence of solicited adverse reactions within 7 days after vaccination.
- The incidence of unsolicited adverse events within 28 days after vaccination.
- The incidence of detectable viral load 24 and 52 weeks after vaccination
- The incidence of serious adverse events (SAE) and medically attended adverse events (MAE) within 52 weeks after vaccination in all participants.

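### The diary for the 28-day unsolicited-AE endpoint can be collected at an in-window visit before the 28 days are over, and no scheduled contact is assigned to complete it

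*Protocol*

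**What the plan says.** The endpoint in Section 9.3.3 is: "The incidence of unsolicited adverse events within 28 days after vaccination". The Synopsis version counts from each dose: "The incidence of unsolicited adverse events within 28 days after each vaccination". Section 7.2 makes recording a duty: "All AEs starting within 28 days following administration of the dose of the study product must be recorded". Table 3 in Section 7 keeps unsolicited events collectable from Day 8 to Day 28.

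The table in Section 7.2 names the e-diary or diary card as the method for unsolicited events. Section 5.1 instructs: "Participants will be asked to record solicited AE for 7 days after receiving the vaccination, and unsolicited AE for 28 days, in their diary". On collection after dose 1 it says: "The completed e-diary and diary cards will be reviewed, and data collected at the 28-Day safety in-person visit". For dose 2: "A new diary will be provided at Day 56 and collected at Day 84".

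Tables 1 and 2 in Section 3.4 put a window of 7 days either side on the Day 28, Day 56 and Day 84 visits as a whole. Section 5.1 repeats this for the blood-sampling visits: "The visit window for immunogenicity in-person visits of Day 28 and Day 84 is +/- 7 days".

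On the four-weekly safety calls, Section 5.1 says participants may report any AE at any time, but "only SAE and MAE will be entered into the eCRF". The Synopsis has the same restriction.

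**The concern.** The endpoint needs 28 days of observation after a dose, but the visit at which the diary is collected may come earlier. A site that sees a participant at Day 21 and takes in the diary has kept to the visit schedule, yet may not meet the recording duty in Section 7.2.

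The resulting error goes one way. An early visit can lose events but cannot add any, so incidence can only be understated. Events that were never collected cannot be restored in the analysis. This matters because Section 1.3 gives the collection of sufficient safety data in people with HIV as the reason for the study.

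**Working it through.** The protocol gives no figure to reproduce here. The check is calendar arithmetic on the stated windows, followed by an illustration under assumptions.

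**Inputs.** Endpoint window: 28 days (Sections 7.2 and 9.3.3). Visit 2: Day 28 ± 7. Visit 3, second injection: Day 56 ± 7. Visit 4: Day 84 ± 7 (Tables 1 and 2).

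**Maximum uncovered time**
- Dose 1: earliest Visit 2 = 28 − 7 = Day 21. Uncovered: 28 − 21 = 7 days, and 7/28 = 25%.
- Dose 2, Visit 4 timed from the actual injection: shortest interval = 28 − 7 = 21 days. Uncovered: 7 days, 25%.
- Dose 2, both windows counted from Day 0: latest injection = 56 + 7 = Day 63; earliest Visit 4 = 84 − 7 = Day 77; interval = 14 days. Uncovered: 14 days, and 14/28 = 50%.

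**Average uncovered time** (assumption: visits spread evenly over whole days in the window)
- Dose 1: 7 of the 15 permitted days precede Day 28. Mean loss = (7+6+5+4+3+2+1)/15 = 28/15 = 1.87 days, or 6.7% of 28.
- Dose 2, both windows from Day 0 and independent: the mean absolute difference of two even spreads over 15 days is (15² − 1)/(3 × 15) = 4.98 days. Half of that is in the early direction: 2.49 days, or 8.9%.

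**Effect on incidence** (assumptions: constant hazard, none of the uncovered events recovered). With true 28-day incidence p and t days covered, the observed incidence is 1 − (1 − p)^(t/28). The protocol gives no p, so a range is shown.

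| Assumed p | Diary ends at 21 days | Diary ends at 14 days |
|---|---|---|
| 10% | 7.6% | 5.1% |
| 20% | 15.4% | 10.6% |
| 30% | 23.5% | 16.3% |
| 40% | 31.8% | 22.5% |
| 50% | 40.5% | 29.3% |

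These columns describe participants at the extremes. At the dose 1 average of 1.87 days lost, t/28 = 26.13/28 = 0.933. For p = 10% the observed value is 1 − 0.9^0.933 = 9.4%, a shortfall of about 0.6 percentage points. For p = 40% it is 1 − 0.6^0.933 = 37.9%, a shortfall of about 2.1 points. If events cluster soon after the dose, the shortfall is smaller still.

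**What could pick up the remaining days.** The next in-person visit after Visit 2 is Day 56, where a new diary is issued; after Visit 4 it is Week 24. The automated weekly message asks about SAEs, MAEs and COVID-19 symptoms (Section 3.3), and the four-weekly calls collect SAEs and MAEs (Section 5.1). None of these is assigned to finish an open diary. Section 3.5 does, however, schedule weekly contacts at Day 35 and Day 91. Day 35 is past day 28 for every early Visit 2. Day 91 = 63 + 28, so it reaches day 28 even after the latest permitted second injection.

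**The case against.** The strongest reply is that the diary is not the only route. Section 7.2 prescribes a non-leading question about changes since the product or the last visit. Section 7.1 defines an unsolicited event by questioning of that kind. Section 6.2 requires intercurrent conditions to be checked and recorded at every contact after the first injection. Section 5.1 has incomplete diaries pursued by telephone or other means, and a 21-day diary is arguably incomplete. It also describes the weekly contacts as prompting reports of any illness symptoms. The SAE/MAE restriction there follows a sentence on calls in Weeks 8 to 52, after the dose 1 period, while Table 3 keeps unsolicited events open to Day 28. An e-diary might simply stay open.

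Much of this stands. A reader might infer that the last week is definitely lost, or that nothing later can recover it; these routes mean the documents do not support that. A reader might also infer that participants seen early will be counted as event-free for the missing days. The protocol does not say so: Section 9.3.3 excludes missing values without imputation, and handling of incomplete observation may be set in an SAP that is not shown. Nor is a 50% loss after dose 2 general. It needs opposite extremes of two windows and a Day 0 anchor that the protocol does not state for this purpose.

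What does not stand is the suggestion that the gap is closed. Questioning at Day 56 relies on recall some weeks later. The telephone provision does not say that a diary collected at an in-window visit counts as incomplete. Nothing says the e-diary remains open, and paper cards are allowed. The weekly symptom reports serve to trigger SARS-CoV-2 testing. In the Synopsis the SAE/MAE restriction is attached to calls throughout the 52 weeks.

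**Conclusion.** The point holds as a gap in the collection process; the 28-day endpoint definition itself is intact. A visit within protocol can leave up to 7 of 28 days uncovered after dose 1, and up to 7 or 14 after dose 2 depending on the anchor for Visit 4. These maxima need no distributional assumption.

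The effect is confined to participants seen early and to events that are neither serious nor medically attended. SAEs and MAEs are followed to Week 52, and the 7-day solicited period ends before any permitted early visit. Under an even spread of visits, constant hazard and no recovery, the average dose 1 shortfall is about 0.6 to 2.1 percentage points for assumed incidences of 10% to 40%. Recovery through other contacts or early clustering of events would reduce it. The average effect is therefore probably small, but its direction is fixed and it is cheap to prevent.

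**What to change.** Keep 7 days either way for the blood draw. In Section 5.1 and Tables 1 and 2, state that the diary stays open until 28 days after the actual injection, for each dose. When the visit falls earlier, require the remaining AEs to be collected and entered in the eCRF at the first scheduled weekly contact on or after that day. Alternatively, set the diary-collection window at 0 to +7 days from day 28 after the actual injection. Reconcile the sentence in the Synopsis and Section 5.1 that limits eCRF entry to SAEs and MAEs with the 28-day recording duty in Section 7.2.

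The cost is protocol and table wording plus one added question at a contact that already takes place, or slightly less scheduling flexibility under the alternative. Under either option the diary covers all 28 days after each dose.
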